### **8.3.5.2. Exposure During Breastfeeding**

An exposure during breastfeeding occurs if:

- A female participant is found to be breastfeeding while receiving or after discontinuing study intervention.
- A female is found to be breastfeeding while being exposed or having been exposed to study intervention (ie, environmental exposure). An example of environmental exposure during breastfeeding is a female family member or healthcare provider who reports that she is breastfeeding after having been exposed to the study intervention by inhalation, or skin contact.

The investigator must report exposure during breastfeeding to Pfizer Safety within 24 hours of the investigator's awareness, irrespective of whether an SAE has occurred. The information must be reported using the CT SAE Report Form. When exposure during breastfeeding occurs in the setting of environmental exposure, the exposure information does not pertain to the participant enrolled in the study, so the information is not recorded on a CRF. However, a copy of the completed CT SAE Report Form is maintained in the investigator site file.

An exposure during breastfeeding report is not created when a Pfizer drug specifically approved for use in breastfeeding women (eg, vitamins) is administered in accord with authorized use. However, if the infant experiences an SAE associated with such a drug, the SAE is reported together with the exposure during breastfeeding.

### **8.3.5.3. Occupational Exposure**

The investigator must report any instance of occupational exposure to Pfizer Safety within 24 hours of the investigator's awareness using the CT SAE Report Form regardless of whether there is an associated SAE. Since the information about the occupational exposure does not pertain to a participant enrolled in the study, the information is not recorded on a CRF; however, a copy of the completed CT SAE Report Form must be maintained in the investigator site file.

### **8.3.6. Cardiovascular and Death Events**

Please refer to [Appendix 7](#) for ECG findings of clinical significance and to [Appendix 3](#) for reporting of deaths.

### **8.3.7. Disease-Related Events and/or Disease-Related Outcomes Not Qualifying as AEs or SAEs**

Not applicable.

### **8.3.8. Adverse Events of Special Interest**

AESIs are examined as part of routine safety data review procedures throughout the clinical trial and as part of signal detection processes.

All AESIs must be reported as an AE or SAE following the procedures described in [Sections 8.3.1](#) through [8.3.4](#). An AESI is to be recorded as an AE or SAE on the CRF. In addition, an AESI that is also an SAE must be reported using the Electronic Data Collection Tool.

#### **8.3.8.1. Cytokine release Syndrome**

**CRS** is a known toxicity of therapeutics that function by activation of immune effector cells. CRS is defined as a supraphysiologic response following any immune therapy that results in the activation or engagement of endogenous or infused T-cells and/or other immune effector cells. Symptoms can be progressive, must include fever at the onset, and may include hypotension, capillary leakage causing hypoxia and end organ dysfunction. Symptoms associated with CRS vary greatly and may be difficult to distinguish from other conditions. The severity of symptoms can be mild to life threatening, thus there should be a high index of suspicion for CRS if these symptoms occur.

The severity of CRS will be assessed according to the ASTCT consensus criteria. See [Appendix 12](#).

For both the priming doses and first full dose (76 mg), premedication for CRS is required (see Section 6.8.1).

#### **8.3.8.2. Immune Effector Cell-Associated Neurotoxicity Syndrome**

**ICANS** is a known toxicity of therapeutics that function by activation of immune effector cells. ICANS is defined as “a disorder characterized by a pathologic process involving the central nervous system following any immune therapy that results in the activation or engagement of endogenous or infused T-cells and/or other immune effector cells. Symptoms or signs can be progressive and may include aphasia, altered level of consciousness, impairment of cognitive skills, motor weakness, seizures, and cerebral edema”. It has been observed following administration of some CAR T-cells and BsAbs, and can occur independently of CRS.

The severity of ICANS will be graded according to the ASTCT consensus criteria. See [Appendix 12](#), Section 10.12.

Additional management for Grade  $\geq 3$  CRS and ICANS is described in Section 9.4.1

### **8.3.8.3. Peripheral Neuropathy**

Peripheral neuropathy is a common complication of MM and its treatment. Peripheral neuropathy can be caused by MM itself, either by the paraneoplastic effects of the monoclonal protein (polyneuropathy is an essential feature of POEMS syndrome) or in the form of radiculopathy from direct compression, and particularly by certain therapies, including IMiDs and proteasome inhibitors. Symptoms are usually symmetric and include paresthesias, numbness, burning sensation and muscle weakness; these are generally mild, but in rare cases can be disabling or even life-threatening. Treatment-emergent peripheral neuropathy symptoms are usually symmetric, distal and progressive.[49] Recently, peripheral neuropathy has been described following administration of BCMA-directed bispecific T-cell engagers.[30]

Peripheral neuropathy (including GBS) is considered an important potential risk of elranatamab.

Work-up for new or worsening Grade  $\geq 2$  peripheral neuropathy should include a neurology consult, imaging (eg MRI of the spine), NCV/EMGs, and lumbar puncture to assess CSF. In consultation with a neurologist, appropriate therapy for peripheral neuropathy (eg, steroids and/or IV immunoglobulin) should be considered.

Closely monitor participants for signs and symptoms of neuropathy following infections or following the administration of any vaccine.

### **8.3.8.4. Lack of Efficacy**

The investigator must report signs, symptoms, and/or clinical sequelae resulting from lack of efficacy. Lack of efficacy or failure of expected pharmacological action is reportable to Pfizer Safety **only if associated with an SAE**.

### **8.3.9. Medical Device Deficiencies**

Not applicable.

### **8.3.10. Medication Errors**

Medication errors may result from the administration or consumption of the study intervention by the wrong participant, or at the wrong time, or at the wrong dosage strength.

Exposures to the study intervention under study may occur in clinical trial settings, such as medication errors.

Safety Event	Recorded on the CRF	Reported Via the Electronic Data Collection Tool to Pfizer Safety Within 24 Hours of Awareness
Medication errors	All (regardless of whether associated with an AE)	Only if associated with an SAE

Medication errors include:

- Medication errors involving participant exposure to the study intervention;
- Potential medication errors or uses outside of what is foreseen in the protocol that do or do not involve the study participant.

Such medication errors occurring to a study participant are to be captured on the medication error page of the CRF, which is a specific version of the AE page.

In the event of a medication dosing error, the sponsor should be notified within 24 hours.

Whether or not the medication error is accompanied by an AE, as determined by the investigator, the medication error is recorded on the medication error page of the CRF and, if applicable, any associated AE(s), serious and nonserious, are recorded on the AE page of the CRF.

Medication errors should be reported to Pfizer Safety within 24 hours on via the Electronic Data Collection Tool only when associated with an SAE

#### **8.4. Pharmacokinetics**

All participants will have blood samples collected for PK assessments of elranatamab serum concentrations at the time points specified in the [SoA](#). In the event of suspected CRS, unexpected or serious AE, or AE leading to discontinuation of study intervention, additional PK samples should be collected if not already scheduled. The actual date/time of sample collection should be documented in the CRF. For each time point, blood samples of approximately 5 mL, to provide a minimum of 2 mL serum, will be collected for measurement of serum concentrations of elranatamab. Instructions for the collection and handling of biological samples will be provided in the laboratory manual or by the sponsor. The actual date and time (24-hour clock time) of PK sample collection will be recorded in the CRF.

The actual times may change, but the number of samples will remain the same. All effort should be made to obtain the samples at the exact nominal time relative to dosing (see [SoA](#)). Collection of samples up to and including 48 hours after dose administration that are obtained within 10% of the nominal time relative to dosing will not be captured as a protocol deviation, as long as the exact time of the collection is noted on the CRF. For predose PK

CCI [Redacted]

[Redacted]

[Redacted]

[Redacted]

[Redacted]

[Redacted]

I [Redacted]

I [Redacted]

I [Redacted]

I [Redacted]

I [Redacted]

I [Redacted]

CCI [REDACTED]

I [REDACTED]

I [REDACTED]

I [REDACTED]

[REDACTED]

[REDACTED]

[REDACTED]

[REDACTED]

[REDACTED]

[REDACTED]

[REDACTED]

[REDACTED]

[REDACTED]

CCI [REDACTED]

---

[REDACTED]  
[REDACTED]

[REDACTED]  
[REDACTED]

[REDACTED]  
[REDACTED]  
[REDACTED]

[REDACTED]  
[REDACTED]

[REDACTED]  
[REDACTED]

[REDACTED]  
[REDACTED]

I [REDACTED]

I [REDACTED]

I [REDACTED]

[REDACTED]

[REDACTED]

## 8.7. Immunogenicity Assessments

Blood samples of approximately 5 mL, to provide a minimum of 2 mL, will be collected for determination of ADA and NAb into appropriately labeled tubes at times specified in the SoA. Instructions for the collection and handling of biological samples will be provided in the laboratory manual. The actual date and time (24 hour clock time) of each sample will be recorded.

Participants having an unresolved AE that is possibly related to anti-ekatanab antibodies at their last assessment will be asked to return to the clinic for ADA and drug concentration blood sampling at approximately 3-month intervals until the AE or its sequelae resolve or stabilize at a level acceptable to the investigator and sponsor.

CCI

Samples will be analyzed using a validated analytical method in compliance with applicable SOPs. Samples determined to be positive for ADA may be further characterized for NAb.

The immunogenicity samples must be processed and shipped as indicated in the instructions provided to the investigator site to maintain sample integrity. Any deviations from the immunogenicity sample handling procedure (eg, sample collection and processing steps, interim storage, or shipping conditions), including any actions taken, must be documented and reported to the sponsor. On a case by case basis, the sponsor may make a determination as to whether sample integrity has been compromised.

As part of understanding the immunogenicity of the investigational product, samples may be used for evaluation of the bioanalytical method and/or additional characterization of an observed immunogenicity response. CCI

## 8.8. Health Economics

Health economics/medical resource utilization and health economics parameters are not evaluated in this study.

## 9. STATISTICAL CONSIDERATIONS

Detailed methodology for summary and statistical analyses of the data collected in this study is outlined here and further detailed in a SAP, which will be maintained by the sponsor. The SAP may modify what is outlined in the protocol where appropriate; however, any major modifications of the primary endpoint definitions or their analyses will also be reflected in a protocol amendment.

## 9.1. Statistical Hypotheses

The primary endpoint of this study is Grade  $\geq 2$  CRS rate for Part 1 & Part 2. No hypothesis for statistical significance will be tested. Instead, a Bayesian design will be used to estimate the true Grade  $\geq 2$  CRS rate in Part 1 and 2. Details are described in Section 9.5.

### 9.1.1. Estimands

#### 9.1.1.1. Primary Estimand

The primary estimand is the treatment effect of elranatamab with a dosing regimen that includes 2 step-up priming doses with premedication on the rate of Grade  $\geq 2$  CRS as assessed by ASTCT criteria. It is defined by the following attributes:

- Population: RRMM participants, as defined by the inclusion and exclusion criteria to reflect the targeted population of the treatment, who received at least one dose of study intervention elranatamab.
- Variable: Incidence of Grade  $\geq 2$  CRS as assessed by ASTCT criteria during C1.

The intercurrent event is treatment discontinuation due to any reason, and is addressed by the treatment condition of interest attribute. All data collected after an intercurrent event of treatment discontinuation will be excluded

- Population-level summary: The median and its corresponding 2-sided 90% credible interval of Grade  $\geq 2$  CRS rate in the analysis population based on the posterior distribution.

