### 2.3.1. Risk Assessment

Potential Risk of Clinical Significance	Summary of Data/Rationale for Risk	Mitigation Strategy
Study Intervention: Elranatamab monotherapy		

CRS
	
A known toxicity of therapeutics that function by activation of immune effector cells.
 
Circulating cytokines are elevated after IV or SC administration of elranatamab. CRS signs and symptoms are expected mainly after the first and second dose and occasionally after the third or later doses of elranatamab.
 
In the present study, elranatamab dose will be increased to > 76 mg starting from Cycle 2 either with longer dosing intervals in Part 2A DLI, Part 2A DL2, and Part 2B CCI [REDACTED]
 
For Part 2, the planned regimen would result in up to 2-fold higher Cmax on Cycle 2 Day 1 (152 mg Q2W) compared to 76 mg QW. Higher Cmax during the first 24 hours of the first
	
Participants will be hospitalized for at least 2 days after the CID1 dose and at least 1 day after the CID4 dose for safety surveillance (Part 1, Part 2). Hospitalization from CID1 to CID5 may be considered. Since CRS events occurred after the first (predominantly within the first 2 days) and second dose of eh-anatamab, the planned 2-day hospitalization after the first dose allows for the detection of initial CRS signs and symptoms and enables timely management of these events according to the ASTCT management guidelines. The 1-day hospitalization on CID4 is considered adequate given the anticipated lower incidence and grade CRS after the second step-up dose of 20 mg.
 
For Part 2A, participants will be hospitalized for at least 1 day also on C2D1. For Part 2B and Part 2C, hospitalization on C2D1 may not be required depending on CRS profile observed in Part 2A. For participants enrolled in Part 1 who would switch to the RP2D Q4W, optional hospitalization may be considered on the day of RP2D administration depending on CRS profile observed in Part 2A and Part 2B.
 
The 2 step-up priming doses schema is expected to mitigate the rate and severity of CRS, which is mainly expected after the first 1 to 2 doses.
 
To further mitigate the CRS risk, premedications will be administered prior to the first 3 doses on CID1, CID4 and CID8 (see Section 6.8.I). No premedications will be administered on C2D1 for Part 2 as the risk of CRS after repeated eh-anatamab administration, even with a higher eh-anatamab dose, is considered low.
 
Guidance for monitoring, grading, and management of CRS per ASTCT criteria and guidelines is included in Appendix 12.
 
Dose modification/discontinuation in the setting of Grade 2 AEs (including CRS) is described in Section 6.5.
 
This study will include only participants who are likely to tolerate potential events of CRS by excluding participants who are particularly susceptible to complications of CRS, including those with impaired cardiac function or clinically significant CV disease (see Section 5.1 and Section 5.2).
 
Criteria for temporary study hold based on Grade 3 CRS events are described in Section 9.4.1.

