**Table 6. Dose Modifications for Elranatamab-Related Toxicity and for Peripheral Sensory or Motor Neuropathy**

Toxicity	Grade 1	Grade 2	Grade 3	Grade 4
Non-hematologic (excluding peripheral neuropathy – see below)	Continue treatment. a	Continue treatment. Alternatively, per investigator discretion, withhold treatment until toxicity is Grade ≤1, then resume. a	Withhold treatment until toxicity is Grade ≤1 or has returned to baseline, then resume treatment. a,b	Permanently discontinue. a,b
Hematologicc,d	Continue treatment.	Continue treatment.	Withhold treatment until toxicity is Grade ≤2 or has returned to baseline, then resume treatment. d	Withhold treatment until toxicity is Grade ≤2 or returns to baseline. d
Peripheral sensory or motor neuropathy (any causality) See Section 8.3.8 for recommended work-up.	Continue treatment.  Continue to monitor the participant for signs of worsening neuropathy. e	For new or worsening Grade 2 peripheral neuropathy withhold treatment until resolution to Grade ≤1, then resume treatment.  Continue to monitor the participant for signs of worsening neuropathy. e  If Grade ≥2 neuropathy reoccurs, permanently discontinue elranatamab.	First occurrence: withhold treatment until neurologic toxicity symptoms improve to Grade ≤1.  Recurrent: permanently discontinue elranatamab.	Permanently discontinue elranatamab

a Both elranatamab priming doses must be administered before the full elranatamab dose. If C1D4 dose cannot be administered on the planned date, elranatamab treatment may restart at the planned 20 mg C1D4 dose upon meeting the re-treatment criteria. If the 20 mg dose is tolerable, elranatamab should then be increased to the full 76 mg dose 1 week later. If after C1D4, a participant experiences a treatment-related adverse event that leads to a dose interruption or delay (ie, dose held on C1D8), elranatamab treatment may restart at the same dose (20 mg) upon meeting the re-treatment criteria (Section 6.5.1). If the 20 mg dose was tolerable, the elranatamab dose should be increased to 76 mg. In case of ongoing CRS or ICANS of any grade on any dosing day, dosing will be held until CRS or ICANS resolution.

b Grade 3 or 4 nausea, vomiting or diarrhea must persist at Grade 3 or 4 despite maximal medical therapy to require dose modification or permanent discontinuation.

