2.1. Study Objectives, Endpoints, and Estimands

Type	Objectives	Endpoints	Estimands
Primary			
Safety	
 To assess the rate of Grade ≥ 2 CRS when elranatamab is administered with a dosing regimen of 2 step-up priming doses and premedication in participants with RRMM. 	
 Grade ≥ 2 CRS rate during C1. 	
 The primary estimand is rate of Grade ≥ 2 CRS during C1 as assessed by ASTCT criteria. It will be estimated based on all enrolled RRMM participants who received at least 1 dose of study intervention regardless of duration on the study treatment.
Secondary			
Safety	
 To assess the safety and tolerability of elranatamab at doses >76 mg with a longer dosing interval (>1 week) in order to identify the RP2D (Part 2A only). 	
 Incidence of DLTs during DLT observation period 	
 The secondary estimand is DLT rate estimate based on data from DLT-evaluable participants during the DLT observation period.

Type	Objectives	Endpoints	Estimands
Safety	
 To evaluate the overall safety profile of elranatamab with 2 step-up priming doses and alternative dosing regimens in participants with RRMM. 	
 Adverse Events as characterized by type, frequency, severity as graded by NCI CTCAE version 5.0, timing, seriousness, and relationship to elranatamab. The severity of CRS and ICANS will be assessed according to ASTCT criteria; Laboratory abnormalities as characterized by type, frequency, severity (as graded by NCI CTCAE version 5.0), and timing. 	
 Not Applicable.
Efficacy	
 To evaluate the anti-myeloma activity of elranatamab with alternative dosing regimens in participants with RRMM. 	
 ORR and CRR, per IMWG response criteria as determined by investigator; Time to event endpoints: TTR, DOR, DOCR and PFS per IMWG response criteria as determined by investigator, and OS; MRD (assessed by central lab) negativity rate per IMWG sequencing criteria. 	
 Not Applicable.
PK	
 To evaluate the PK of elranatamab 	
 Pre- and postdose concentrations of elranatamab. 	
 Not Applicable.

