3.4. Baseline Variables

Start and end dates of study intervention:

The date of first dose (start date) of study intervention is the earliest date of nonzero dosing of the study drug.

The date of last dose of study intervention is the latest date of the nonzero dosing of the study drug.

Definition of baseline:

No windowing will be applied when defining baseline. For example, the protocol requires safety assessments to be performed within 28 days prior to first dose; however, values outside this window will not be excluded when determining baseline assessments. Any deviations from the protocol specified window will be documented as protocol deviations. A separate definition of adequate baseline ([Section 5.2.9](#)) is provided for disease assessment related efficacy endpoints.

For all endpoints, the last assessment performed on or prior to the date of the first dose of study intervention will serve as the baseline assessment. If there are no observations meeting these criteria, then baseline is considered missing.

Participants who start treatment and discontinue from the study on the same day may have 2 different sets of data collected on Study Day 1 (one during study and one in the End of Treatment [EOT] visit). Data reported at the EOT visit are not eligible for baseline selection.

Triplicate ECGs are collected at all timepoints except screening (single ECG at screening); therefore, the baseline for ECG measurement is the pre-dose on Cycle 1 Day 1, or the most recent ECG assessment reported prior to the first administration of study drug. Unscheduled assessments will not be included in the calculation of the average. The average of the replicate measurements will be determined after the derivation of the individual parameters at each timepoint.

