5.2.5. Definition of Cycle and Cycle Day

Cycle start and end dates are derived per participant. The definition for each cycle is driven by the study intervention elranatamab. Elranatamab is administered in a 28-day cycle.

- For Cycle 1, the actual cycle start date is the date each participant receives the first non-zero study intervention;
- For all other cycles, the actual cycle start date for each participant is the earliest start date of dosing in the Cycle X Day 1 visit CRF exposure page;
- For all but the last cycle:
 - Actual cycle stop date is calculated as the start date of the next cycle minus 1 day;
 - Actual cycle duration is calculated from Day 1 of a cycle to the day prior to Day 1 of the next cycle, as follows:

$$\text{Actual Cycle Duration (weeks)} = (\text{cycle stop date} - \text{cycle start date} + 1)/7$$

- For the last cycle, actual cycle duration is the planned cycle duration and actual cycle stop date is calculated as actual cycle start date + 28 – 1 day.

The cycle day will be calculated as:

$$\text{Cycle day} = \text{Date of the assessment/event} - \text{cycle start date} + 1.$$

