5.2.7. Date of Last Contact

The date of last contact will be derived for participants not known to have died at the data cutoff date using the latest complete date (ie, imputed dates will not be used in the derivation) among the following:

- All assessment dates (eg, blood draws [safety laboratory, Pharmacokinetics (PK), CCI and immunogenicity], vital signs, physical exam, neurological exam, performance status, ECG, Echocardiograms [ECHO]/multigated acquisition [MUGA] scans, disease assessments, etc.);
- Start and stop dates of concomitant therapies including non-drug treatments or procedures;
- Start and end dates of new therapies administered after study intervention discontinuation including systemic therapy and radiation;
- AE start and end dates;
- Last date of contact collected on the ‘Survival Follow-up’ CRF (do not use date of survival follow-up assessment unless status is ‘alive’);
- Study intervention start and end dates;
- Date of discontinuation on disposition CRF pages (do not use if reason for discontinuation is lost to follow-up or death).

Only dates associated with actual examinations of the participant will be used in the derivation. Dates associated with a technical operation unrelated to participant status such as the date a blood sample was processed or dates when data were entered into the CRF will not be used. Assessment dates after the data cutoff date will not be applied to derive the last contact date.

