6.1. Primary Endpoints

The primary endpoint is Grade ≥ 2 CRS rate during Cycle 1, defined as the proportion of participants in the Safety Analysis Set experiencing Grade ≥ 2 CRS as assessed by ASTCT criteria.

Estimand strategy: All data collected after the intercurrent event of treatment discontinuation due to any reason will be excluded in the analysis.

Analysis set: Safety Analysis Set (as defined in [Section 4](#)).

Intercurrent events and missing data: The intercurrent event is treatment discontinuation due to any reason. No imputations for missing data will be performed.

Analysis methodology: The median and its corresponding 2-sided 90% credible interval based on the posterior distribution of Grade ≥ 2 CRS rate will be calculated. In addition, point estimates of Grade ≥ 2 CRS rate will be calculated along with the 2-sided 90% CIs using the Clopper-Pearson method⁸ (exact CI for a binomial proportion).

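### The primary analysis drops data after treatment discontinuation but keeps every treated participant in the denominator, so it can only lower the Cycle 1 Grade ≥2 CRS count; the date that triggers the rule is not specified

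*Protocol*

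**What the plan says.** Protocol 9.1.1.1 names treatment discontinuation for any reason as the intercurrent event and states: "All data collected after an intercurrent event of treatment discontinuation will be excluded". SAP 6.1 agrees: "All data collected after the intercurrent event of treatment discontinuation due to any reason will be excluded in the analysis". It adds that missing data are not imputed.

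The endpoint is a proportion of the Safety Analysis Set, which is everyone who received at least one dose (protocol 9.2 and 9.3.2; SAP 4 and 6.1). By default, missing observations stay in denominators (SAP 5.2.13).

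The objectives table describes the same estimand as covering all participants "who received at least 1 dose of study intervention regardless of duration on the study treatment" (SAP 2.1; also protocol section 3).

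Two dates could mark discontinuation, and neither is linked to the exclusion rule:

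- SAP 3.4: "The date of last dose of study intervention is the latest date of the nonzero dosing of the study drug".
- SAP 5.2.7, in the list of sources for the date of last contact: "Date of discontinuation on disposition CRF pages".

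SAP 5.2.5 fixes the length of Cycle 1 for someone who stops early: "For the last cycle, actual cycle duration is the planned cycle duration". The window therefore runs to Day 28 whether or not dosing continues.

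**The concern.** The stated variable is incidence during Cycle 1 in all treated participants. The exclusion rule measures something narrower: incidence up to discontinuation, divided by all treated participants, with everyone who stopped early treated as event-free from then on. The same CRS event could appear in the safety tables, because the on-treatment period in SAP 3.5 extends up to 90 days after the last dose, and yet be missing from the primary count.

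Protocol 9.1.1.1 also says the intercurrent event is handled through a treatment-condition attribute. It lists no such attribute for the primary estimand, although 9.1.1.2 lists one for the secondary.

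What is at stake is the GO/No-GO decision and the interim futility check, both of which use this count. The DLT model and the enrollment-hold rules are separate and unaffected. Because the date is open, the count may also depend on a choice made after the data can be seen in an open-label trial.

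**Working it through.** **Inputs.** Prior Beta(0.7, 1.3). GO requires P(rate > 35%) < 10% and a posterior median ≤ 27%. N = 76 with at most 20 events (protocol 9.5.1). Futility at 11 or more of 30, from a predictive probability below 10% (protocol 9.4.2, SAP 7.2.2). Second-stage size 76 − 30 = 46.

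**Step 1: reproduce the plan.** The posterior is Beta(0.7 + r, 1.3 + 76 − r).

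- r = 20: median 0.2634, P(> 35%) = 0.0509, so GO.
- r = 21: median 0.2763, P(> 35%) = 0.0828, so No-GO, failing on the median alone.

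With X1 ~ Bin(30, p) and X2 ~ Bin(46, p), P(futility) = P(X1 ≥ 11) and P(GO) = Σ over x = 0 to 10 of P(X1 = x)·P(X2 ≤ 20 − x). This gives P(GO) = 0.4877 at p = 0.27 and 0.0652 at p = 0.35, with P(futility) = 0.4922 at 0.35. All 18 entries of protocol Table 12 are reproduced to within 0.001. The beta-binomial predictive probability of ending with 20 or fewer events is 0.164 at 10/30 and 0.067 at 11/30, which matches the stated boundary.

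**Step 2: direction.** With a fixed denominator and no imputation, deleting records can turn an event into a non-event but not the reverse. The count falls or stays the same.

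**Step 3: what the date decides.** Take a participant dosed only on C1D1 who has Grade 2 CRS in the following two days and is taken off treatment at C1D4.

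- Disposition date: the event precedes discontinuation and counts.
- Last-dose date: the event falls after C1D1 and is dropped.

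Protocol 2.3.1 places CRS after the first dose "predominantly within the first 2 days", which is mostly after the last-dose date for such a participant.

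**Step 4: size of one lost event.** If one second-stage event is dropped, 21 true events still read as GO:

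| True rate | P(GO), all events counted | P(GO), one second-stage event dropped |
|---|---|---|
| 27% | 0.488 | 0.576 |
| 30% | 0.274 | 0.354 |
| 35% | 0.065 | 0.100 |

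If one event among the first 30 is dropped, a true 11/30 is read as 10/30, so the predictive probability moves from 0.067 (may stop) to 0.164 (continue). P(futility) at a true 35% falls from 0.492 to 0.345.

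The limit is to be updated for the actual N. The maximum for GO is 19 at N = 74, 20 at N = 75 to 77, and 21 at N = 78, so the same one-event edge exists at each.

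**Step 5: illustration with assumed loss fractions.** The documents give no figure, so let a share q of true events be lost at a true 35% (76 × 0.35 = 26.6 expected events). The counted rate is then 0.35 × (1 − q).

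| q (assumed) | Expected events lost | P(GO) |
|---|---|---|
| 0 | 0 | 0.065 |
| 1% | 0.3 | 0.074 |
| 2% | 0.5 | 0.083 |
| 5% | 1.3 | 0.115 |
| 10% | 2.7 | 0.190 |

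**The case against.** The strongest reply is that the disposition date is the natural reading. SAP 5.2.7 lists it separately from the dosing dates, and the last-dose date is never called discontinuation. On that reading an event is lost only if a participant permanently stops in Cycle 1 and first reaches Grade ≥2 CRS afterwards, still within the cycle. That should be rare. CRS is expected mainly after the first doses, and in the earlier study's subcutaneous cohorts only 2 of 50 had CRS after the second dose and none after later ones (protocol 4.3.1, under different priming). CRS ordinarily leads to a hold: "In case of ongoing CRS or ICANS of any grade on any dosing day, dosing will be held until CRS or ICANS resolution". CRS severe enough to force a stop would come before it and so be counted. This stands, and it means the loss may be near zero. It does not settle which date applies, because the text does not say.

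Second, a while-on-treatment approach is a recognised strategy, and the objectives-table wording could be read as describing who is included rather than which data are used. But neither document names that strategy, and CRS after the last dose is still an effect of the priming regimen the estimand is meant to measure.

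Third, the CRS summaries in SAP 6.8.1.1 would still show such events. That gives visibility but does not correct the primary count.

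Fourth, futility is non-binding, and protocol 4.1 reports enrollment complete at Amendment 4, so the interim figures probably have no remaining decision to affect. The figures in Step 4 assume that one event is lost, and the fractions in Step 5 are assumed. Both points are accepted.

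**Conclusion.** The concern holds and should be fixed. The direction is certain: the rule can only move the primary result towards GO and the interim away from futility. The size is not known from the documents. It may be zero on the disposition-date reading and larger on the last-dose reading. The design has no slack at its boundary, so a single excluded event is enough to reverse a No-GO at 21 of 76. This conclusion rests on the denominator remaining the full Safety Analysis Set with no imputation, as both documents state.

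**What to change.** Replace the exclusion sentence in protocol 9.1.1.1 and SAP 6.1 with a treatment-policy rule: count every Grade ≥2 CRS from first dose to the end of Cycle 1, whether or not treatment was stopped, with Day 28 as the end for anyone who discontinues in Cycle 1. Keep the current rule as a sensitivity analysis and state whether its date is the last dose or the disposition date. Report how many participants have incomplete Cycle 1 follow-up because they withdrew consent, since AE collection ends then (protocol 8.3.1). If the primary analysis has already been run, report the treatment-policy count beside it.

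The cost is a short amendment and a SAP update; protocol section 9 calls for an amendment when the primary analysis changes in a major way. AEs are already collected for at least 90 days after the last dose, so no new data are needed. The reported CRS rate may be slightly less favourable.
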